#### 3.3. DOSING

#### 3.3.1. Dosing Regimen

The dosing regimen will be a single dose treatment injection of RZL-012 in multiple sites.

The first 6 subjects randomly assigned to the RZL-012 treatment group (cohort 1) will initiate at the dose of 40 mg RZL-012 (approximately 1/6.25th the NOAEL as determined in the GLP toxicology study) and 2 more subjects will be given placebo (vehicle).

If no more than 1 subject experiences intolerable side effects within the 1st cohort, 14 days following the injection of the last dosed subject, an additional 6 subjects will receive a dose of 80 mg RZL-012 (approximately 1/3.125th of the NOAEL) and 2 more subjects will be given placebo (vehicle).

If no more than 1 subject experiences intolerable side effects within the 2nd cohort, 14 days following the injection of the last dosed subject, an additional 6 subjects will receive a dose of 120 mg RZL-012 (approximately1/2.34th of the NOAEL) and 2 more subjects will be given placebo (vehicle).

If no more than 1 subject experiences intolerable side effects within the 3rd cohort, 14 days following the injection of the last dosed subject, according to schedule an additional cohort of 6 volunteers, as above, will receive 180 mg RZL-012 (1/1.39 of the NOAEL). Additional 2 subjects in the cohort will serve as control and will be injected placebo (vehicle).

Dosing of the first 3 subjects in each cohort will progress consecutively from one individual to the other at 7-day intervals. For additional precaution, the first 3 subjects will be forced randomization with 2 active and 1 control. This study design will allow the physicians to monitor safety in a single subject at each dose; nevertheless, the blindness will remain intact.

The next subjects in the cohort will be randomized to either active treatment or placebo in a ratio determined by the number of subjects targeted for each cohort. Dosing of the next subjects will be in couples and the last subjects will be in a triplet.

If 1 subject had already experienced intolerable side effects in a cohort, then enrollment will progress consecutively from one individual to the other at 7-day intervals until that cohort is complete.

The trial will proceed within a cohort and from one cohort to the next as long as no more than one subject experiences intolerable side effects in the lower-dose cohort, and based on the decision made by a DSMB. The decision to proceed to the next cohort will be made after reviewing all safety data collected by Day 14 within  $2 \pm 1d$  of the last dosed subject in each cohort. The DSMB will be comprised of two independent medical doctors (MDs) expert in early phase clinical trials.

#### 3.3.2. Intolerable Side Effect

Safety will be the principal primary endpoint of this study, as such if there are 2 intolerable and at least possibly related side effects observed in any dose cohort, that dose cohort will be stopped and only tolerable doses used for future subjects.

An intolerable side effect defined as any of the following treatment-related adverse drug reactions (ADRs):

- Any Grade 3 or greater event except for the following (For the following entities, a discussion will be held by the PI, DSMB and Sponsor to decide whether considered as an intolerable side effects):
  - o Flu-like symptoms and fever that responds to standard treatment within 72 hours
  - Localized edema and erythema
  - o Pruritus
  - o Pain
  - Skin/soft tissue inflammation
  - Fat Atrophy
  - o Liver enzymes abnormality

# o Non-significant lab abnormalities, lasting less than 7 days

To establish a threshold for clinical abnormalities and liver enzyme abnormalities the following tables were formed for main expected side effects. For the following abnormalities, intolerable side effect would be any Grade 3 or greater event:

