#### Intolerable Side Effect Definition

Safety will be the principal primary endpoint of this study, as such if there are 2 intolerable and at least possibly related side effects observed in any dose cohort, that dose cohort will be stopped and only tolerable doses used for future subjects

An intolerable side effect defined as any of the following treatment-related adverse drug reactions (ADRs):

- Any Grade 3 or greater event except for the following (For the following entities, a discussion will be held by the PI, DSMB and Sponsor to decide whether considered as:intolerable side effects):
  - o Flu-like symptoms and fever that responds to standard treatment within 72 hours
  - Localized edema and erythema
  - o Pruritus
  - o Pain
  - Skin/soft tissue inflammation
  - o Fat Atrophy
  - Liver enzymes abnormality
  - o Non-significant lab abnormalities, lasting less than 7 days (see Section 3.3.2)

Study discontinuation is to be considered by the investigator in any case of an intolerable side effect, and the actions taken are to be fully documented in source documents and Case Report Forms (CRFs).

To be considered an intolerable side effect, such an event must be considered to be possibly or probably related to the study drug

Subjects experiencing an intolerable side effect will be withdrawn from the study, but followed for toxicity.

The study may also be prematurely terminated in any of the following cases:

- Recurring serious or severe adverse drug reaction (ADR) clinically evaluated by DSMB as warranting study termination.
- A decision made by Sponsor and/or IRB/EC and/or local regulatory agency to terminate the study.

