#### **Clinical Abnormalities Table**

Local Reaction to Injectable Product	Mild (Grade 1)	Moderate (Grade 2)	Severe (Grade 3)	Potentially Life Threatening (Grade 4)
Pain	Does not interfere with activity Repeated use of non-narcotic pain reliever > 24 hours	activity	Any use of narcotic pain reliever beyond 7 days following injection or prevents daily activity	Emergency room (ER) visit or hospitalization
Tenderness	Discomfort to touch or with movement	Significant discomfort at rest	Prevents daily activity	ER visit or hospitalization
Erythema/Redness *	2.5 - 7 cm	7.1 - 15 cm	> 15 cm	Necrosis or exfoliative dermatitis
Induration/Swelling **	2.5 - 7 cm and does not interfere with activity	7.1 - 15 cm or interferes with activity	> 15 cm or prevents daily activity	Necrosis

\* Erythema – the measured local reaction at the greatest single diameter beyond the injected area surface of all injections (4x8 cm for the first cohort, 8x8cm for the second cohort and 12x8cm for the third and fourth cohort), the measurement should be recorded as a continuous variable.

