#### 6.1.8.2. Serum Chemistry Analysis

Testing of blood chemistry values will be conducted at screening Day 1 (performed 28 through 7 days prior to baseline) in order to ensure compliance with study inclusion criteria. At screening Day 1, subjects should be notified to come fasting (10-12 hours of fast) for fasting glucose, blood test.

Additional fasting glucose, insulin, leptin, lipid profile blood tests will be conducted at clinic admission visit (Day -1) and on study visit Day 28 and every 28 days during follow-up period.

Additional Serum Chemistry testing will be conducted at clinic admission visit (Day -1) to establish baseline values,  $24hr \pm 2hr$  following injection and on study visit Day -1, 1, 3, 7, 14 and 28.

Serum chemistry will include: Sodium, Calcium, Potassium, Phosphorus, Glucose, Liver enzymes (Aspartate aminotransferase [AST], Alanine aminotransferase [ALT], Lactate dehydrogenase [LDH], Creatine-kinase MM [CK-MM], Gamma-glutamyltransferase [GTTP], Alkaline phosphatase [ALP]), Bilirubin, Creatinine, Urea/Blood urea nitrogen [BUN], Total protein, Albumin, Amylase, Creatine phosphokinase [CPK]

Lipid profile will include: (Triglycerides [TG], High-density lipoprotein [HDL], Low-density lipoprotein [LDL], Total-cholesterol [TC] and Free-fatty-acids [FFA]).

In case of CK-MM >x5 ULN, subjects will undergo clinical assessment for symptoms and alternative causes, and renal function will be assessed (including urinalysis).

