#### 9.2. ADVERSE EVENT GRADING

AE will be documented and graded according to the National Cancer Institute Common Terminology Criteria for Adverse Events (CTCAE) v4.03 June 14, 2010) (10).

AE that do not appear in the CTCAE will be graded as follows:

- Mild (Grade 1): Sign or symptom, usually transient, requiring no special treatment and generally not interfering with usual activities.
- Moderate (Grade 2): Sign or symptom, which may be ameliorated by simple therapeutic measures, may interfere with usual activity.
- Severe (Grade 3): Sign or symptom that is intense or debilitating and that interferes with usual activities and/or requires hospitalization. Recovery is usually aided by therapeutic measures and the discontinuation of the study product may be required.
- Life-threatening or disabling (Grade 4): Sign or symptom that is Life-threatening or disabling.
- Death (Grade 5): Death related to AE

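### Protocol 3.3.2: the cohort 4 grading area does not fit its injection grid, the stop rule counts events in some places and subjects in others, and no sentence ranks the grading tables against the discussion list

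*Protocol*

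**What the plan says.** Protocol 3.3.2 and the synopsis (Intolerable Side Effect Definition) start from one rule: a treatment-related event of Grade 3 or more is intolerable. Eight listed entities are excepted, among them pain, localized edema and erythema, skin/soft tissue inflammation and liver enzyme abnormality. For these, "a discussion will be held by the PI, DSMB and Sponsor to decide whether considered as an intolerable side effects".

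Directly after the list, 3.3.2 brings in two tables: "To establish a threshold for clinical abnormalities and liver enzyme abnormalities the following tables were formed for main expected side effects". It continues: "For the following abnormalities, intolerable side effect would be any Grade 3 or greater event". The first table, headed "Local Reaction to Injectable Product", has rows for pain, tenderness, erythema and induration/swelling. The second covers ALT and AST. The synopsis carries only the discussion route; its pointer to 3.3.2 hangs on the last listed entity, non-significant laboratory abnormalities. The general scale is in Protocol 9.2: "AE will be documented and graded according to the National Cancer Institute Common Terminology Criteria for Adverse Events".

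The table footnotes measure erythema and induration outside the injected area, given as 4x8 cm (cohort 1), 8x8 cm (cohort 2) and 12x8 cm (cohorts 3 and 4). The synopsis and Protocol 6.2.3.1 place the injections 2 cm apart in cohorts 1 to 3. In cohort 4 they form a 9x4 grid 1 cm apart.

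SAP 5.3.4 and 5.8.13 use the term intolerable side effect for the primary safety endpoint, with exact 95% intervals by cohort, and do not define it.

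**The concern.** Whether an event counts as intolerable decides several things at once: stopping or proceeding, one-by-one dosing after a first case (Protocol 3.3.1), withdrawal (3.3.2), replacement within 28 days in cohorts 3 and 4 (5.4), and the numerator in SAP 5.8.13. With six active subjects per cohort, one subject is decisive.

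The tabulated events are the ones the protocol itself expects most. Protocol 1.2.4 reports one severe ALT elevation in phase 0 (arm not stated), where the top dose was 20 mg; this trial starts at 40 mg. A wrong reference area, two units for the stop rule and an unranked pair of routes all act on these events.

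**Working it through.** **(a) Cohort 4 area.** Inputs: grids and spacing from the synopsis and Protocol 6.2.3.1, stated areas from the 3.3.2 footnotes. Three conventions were tried for each side with n injection points.

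| Cohort | Grid, spacing | n x spacing | (n-1) x spacing + 2 cm | (n-1) x spacing | Stated |
|---|---|---|---|---|---|
| 1 | 2x4, 2 cm | 4x8 | 4x8 | 2x6 | 4x8 |
| 2 | 4x4, 2 cm | 8x8 | 8x8 | 6x6 | 8x8 |
| 3 | 6x4, 2 cm | 12x8 | 12x8 | 10x6 | 12x8 |
| 4 | 9x4, 1 cm | 9x4 | 10x5 | 8x3 | 12x8 |

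The first two conventions reproduce cohorts 1 to 3 exactly; neither gives 12x8 for cohort 4. In area, 12 x 8 = 96 cm² is stated, against 9 x 4 = 36 cm² (96/36 = 2.7) or 10 x 5 = 50 cm² (96/50 = 1.9).

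The direction of the error depends on orientation:
- Matching long side to long side, the stated area is too large by 12 - 9 = 3 or 12 - 10 = 2 cm, and by 8 - 4 = 4 or 8 - 5 = 3 cm.
- Matching by the grid line in Protocol 6.2.3.1 (up to four marks on the line in cohorts 1 to 3, nine in cohort 4), it is too small along the line by 9 - 8 = 1 or 10 - 8 = 2 cm. Across the line it is too large by 12 - 4 = 8 or 12 - 5 = 7 cm.

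These differences halve if spread is measured from one edge of a centred area. For scale, Grade 2 erythema runs from 7.1 to 15 cm.

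**(b) Unit of the stop rule.**

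| Place | Unit |
|---|---|
| Synopsis, Intolerable Side Effect Definition; Protocol 3.3.2 | two side effects |
| Protocol 3.3.1, 4.1, 10.2.1; SAP 5.3.4 | two subjects or patients (3.3.1: proceed with no more than one) |
| Synopsis, Study Design | both |

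One subject with, say, Grade 3 pain and Grade 3 swelling meets the first rule and not the second.

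**(c) Two routes.** Three of the eight list entries meet four of the five table rows: pain with pain; localized edema and erythema with erythema and, by meaning, induration/swelling; liver enzyme abnormality with ALT/AST. A fourth entry, skin/soft tissue inflammation, also overlaps erythema and induration by meaning.

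The list does not become empty if the tables prevail. The first table covers local reactions only, so pain elsewhere stays on the list. Four of the six liver enzymes in Protocol 6.1.8.2 (LDH, CK-MM, GTTP, ALP) are outside the second table, and CK-MM has its own step: "In case of CK-MM >x5 ULN, subjects will undergo clinical assessment for symptoms and alternative causes".

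Effect of one subject in six active (Clopper-Pearson 95%):
- 1/6 = 16.7% (0.4 to 64.1%): proceed.
- 2/6 = 33.3% (4.3 to 77.7%): stop.

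The documents give no rate q of overlapping Grade 3+ events per subject. Assuming values, P(2 or more of 6) = 1 - (1-q)^6 - 6q(1-q)^5. At q = 10% this is 1 - 0.5314 - 0.3543 = 11.4%.

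| Assumed q | 1 or more of 6 | 2 or more of 6, all counted | 2 or more, if each event has a 50% chance of being counted |
|---|---|---|---|
| 5% | 26.5% | 3.3% | 0.9% |
| 10% | 46.9% | 11.4% | 3.3% |
| 20% | 73.8% | 34.5% | 11.4% |
| 30% | 88.2% | 58.0% | 22.4% |

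If the discussion counts none, the stop probability from these events is zero. With no other intolerable events, the all-counted column is an upper bound on how often the two routes disagree about stopping.

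**The case against.** The strongest reply is that 3.3.2 can be read without contradiction. A listed event that is CTCAE Grade 3 goes to discussion; one that reaches Grade 3 on the study's own table is automatic. The stated purpose of the tables, setting a threshold, supports this. It stands as the likely intent, so a reader who infers that the section contradicts itself goes too far. What remains is that no sentence says so, and the synopsis shows only one route. The same reading also limits the remedy: a sentence that confined the discussion to events outside the tables would take it away from CTCAE Grade 3 pain, erythema or ALT/AST events below table Grade 3.

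Four other inferences are tempting and are not supported:
- That the oversized area under-grades reactions at the top dose. Along the grid line it is slightly too small. Necrosis, and swelling that prevents daily activity, are graded regardless of size. The figures showing the layout are not in the copy reviewed.
- That the routes would disagree in a large share of cohorts. The rates are assumed, and the discussion may reach the same answer as the tables. The rule also applies to blinded cohorts of eight, not only to the six active subjects.
- That dose escalation is unprotected. Every step needs a DSMB decision on the safety data, and the DSMB takes part in the discussion. This does not settle which events SAP 5.8.13 counts.
- That the SAP leaves out related Grade 3+ events by cohort. SAP 5.8.11 and the title of Table 14.3.1-4 speak of treatment group, where Protocol 10.5.7 says by cohort. Only titles are visible, however, and Listing 16.2.7-1 covers adverse events.

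Version also matters. The SAP follows protocol V1.4 of 4 March 2018, while the protocol reviewed is numbered 001.2 with May 2017 footers. The text may have changed since.

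**Conclusion.** The point holds in three parts for the protocol text supplied.

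The cohort 4 area is wrong as written: 96 cm² against 36 or 50 cm², 1.9 to 2.7 times too large. Its net effect on grades depends on orientation and on how spread is measured, neither of which the footnotes settle.

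The stop rule has two units that give different answers for one subject with two events.

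The order of precedence between tables and discussion is missing rather than contradictory. It matters because one classification separates 1/6 from 2/6. How often that would happen cannot be derived from the documents, so the probabilities above are illustrations only.

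The corrections are worth making because they feed Grade 3 classification, dose stopping and the primary safety endpoint. Confidence is medium, mainly because V1.4 was not available. The Grade 3 ALT/AST cell is unreadable in this copy, and nothing here relies on it.

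**What to change.** Check protocol V1.4 first. If the text is unchanged:

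1. In both 3.3.2 footnotes, replace 12x8 cm for cohort 4 with the actual footprint: 9x4 cm, or 10x5 cm if a 1 cm margin is intended. State how spread beyond it is measured and which side lies along the grid line.
2. Count subjects, not events, in the synopsis (Study Design and Intolerable Side Effect Definition) and in 3.3.2. This is the less strict of the two rules, so the DSMB should agree to it.
3. Add to 3.3.2 and the synopsis: related events that reach Grade 3 or above in either table are intolerable however they are termed, including local reactions recorded as skin/soft tissue inflammation. Listed events that are CTCAE Grade 3 or above but below table Grade 3, or that are not in the tables, go to the discussion by the investigator, DSMB and sponsor. Leave the list itself unchanged: deleting pain or liver enzymes would make non-local pain and the other four enzymes automatically intolerable at Grade 3.
4. In SAP 5.8.13 report, by cohort, subjects with any related Grade 3+ event beside subjects with an intolerable side effect, each with its exact interval.

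Cost: one clarifying statement in two places, subject wording in three, one corrected area in two footnotes, and one added row in SAP Table 14.3.1-2. No new visits, subjects or procedures. If the sponsor means the discussion to govern tabulated events as well, item 3 should say that instead; item 4 is useful either way.

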#### **Clinical Abnormalities Table**

Local Reaction to Injectable Product	Mild (Grade 1)	Moderate (Grade 2)	Severe (Grade 3)	Potentially Life Threatening (Grade 4)
Pain	Does not interfere with activity Repeated use of non-narcotic pain reliever > 24 hours	activity	Any use of narcotic pain reliever beyond 7 days following injection or prevents daily activity	Emergency room (ER) visit or hospitalization
Tenderness	Discomfort to touch or with movement	Significant discomfort at rest	Prevents daily activity	ER visit or hospitalization
Erythema/Redness *	2.5 - 7 cm	7.1 - 15 cm	> 15 cm	Necrosis or exfoliative dermatitis
Induration/Swelling **	2.5 - 7 cm and does not interfere with activity	7.1 - 15 cm or interferes with activity	> 15 cm or prevents daily activity	Necrosis

\* Erythema – the measured local reaction at the greatest single diameter beyond the injected area surface of all injections (4x8 cm for the first cohort, 8x8cm for the second cohort and 12x8cm for the third and fourth cohort), the measurement should be recorded as a continuous variable.

# **Liver Enzyme Abnormalities Table**

Serum *	Mild (Grade 1)	 (Grade 3)	Potentially Life Threatening (Grade 4)
Liver Function Tests –ALT, AST increase by factor	3 x ULN		> 10 x ULN beyond 10 days

Study discontinuation is to be considered by the investigator in any case of an intolerable side effect, and the actions taken are to be fully documented in source documents and Case Report Forms (CRFs).

\*\*Induration — the measured local reaction at the greatest single diameter beyond the injected area surface of all injections (4x8 cm for the first cohort, 8x8cm for the second cohort and 12x8cm for the third and fourth cohort), the measurement should be recorded as a continuous variable.

To be considered an intolerable side effect, such an event must be considered to be possibly or probably related to the study drug.

Subjects experiencing an intolerable side effect will be withdrawn from the study, but followed for toxicity.

The study may also be prematurely terminated in any of the following cases:

- Recurring serious or severe ADR clinically evaluated by DSMB as warranting study termination.
- A decision made by Sponsor and/or IRB/EC and/or local regulatory agency to terminate the study.

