# 5.4. REMOVAL, REPLACEMENT OR EARLY WITHDRAWAL OF SUBJECTS FROM ASSESSMENT NOT DUE TO INTOLERABLE SIDE EFFECTS

In the first and second cohorts, if only one subject is withdrawn or removed from the study, and no more than one subject experience intolerable side effects, then the subject will not be replaced. If more than one subject is withdrawn or removed from the study, and more than one subject experience intolerable side effects, then the subject will be replaced by new subject.

In the third and fourth cohort, any withdrawal or removal not due to intolerable side effects within the first 28 days will be replaced by a new subject.

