#### 6.1.17.2.2. Local Fat Mass Reduction

Local reduction in fat mass will be evaluated by MRI. A local fat reduction is defined as a significant reduction (compared to baseline) in the average width of abdominal subcutaneous fat in the injected area compared to the contra-lateral area, SFM ratio, as evaluated by MRI. Local fat reduction in cohort 4 will be defined as a significant reduction (compared to baseline) in the average width of abdominal subcutaneous fat in the injected area compared to the surroundings area, SFM ratio, as evaluated by MRI. MRI will be evaluated in all groups at baseline and at Day 28. MRI will be evaluated in the cohort 3 (or in cohort 2 if 2 subjects will experience intolerable side effects within the 3rd cohort) and cohort 4 every 28 days for up to 6 months from the beginning of treatment.

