### 9.5. ADVERSE EVENT REPORTING AND MONITORING REQUIREMENTS

#### **9.5.1.** General

All adverse events, serious and non-serious, will be fully documented in both source documents and CRFs as described in Section 6.1.16, and each AE will be assessed in light of its clinical significance. For each adverse event, the investigator will provide the onset, end, intensity, treatment required, outcome, seriousness and action taken with the investigational drug. The investigator will determine the relationship to the investigational drug, i.e., causality assessment, for each AE.

Any AE occurring prior to initiation of first dose, after initiation of the first dose and or during any point throughout the study should be recorded on the Adverse Event page of the CRF. All adverse events occurring until subject is terminated from the study (28 days after the injection of RZL-012 and in the highest dose cohort until 6 months from injection of RZL-012), should be captured in the CRF. AEs should be recorded in the CRF using the medical terminology found in the source documentation. Whenever possible, diagnoses should be given when signs and symptoms are due to a common etiology.

Occurrence of any Grade 4 and Grade 3 or 4 ADR must warrant clinical evaluation by the treating investigator and reported to the Sponsor within 7 calendar days.

ADRs graded > 1 will be followed-up until resolution, or for a maximal duration of 6 months after RZL-012 injection, whichever occurs first.

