#### 10.5.5. Efficacy Analysis

The average temperature will be presented in a tabular form by visit, site (treated / not treated) and treatment received (RZL-012 / placebo) by cohort and overall. Difference between the sites (treated – not treated) will be presented in a tabular form by visit treatment along with the change from baseline (net-delta) in these differences by cohort and overall.

Non-parametric tests will be used to compare the net-delta between the study arms for the relevant cohorts and visits.

The number and percent of subjects with a thermogenic effect, defined as a net-delta  $\geq 1$ , will be presented by cohort and visit for the subjects in the active arm. The duration of the thermogenic effect after the Day 28 visit, for subjects in the active arm with thermogenic effect at the Day 28 visit will be presented.

Subcutaneous Fat Mass (SFM) ratio (treated sites / control sites) averaged over the MRI slices will be presented in tabular form by visit, treatment and cohort. The change from baseline in this ratio (in % from the ratio at baseline) will be presented in the same manner, and compared between the treatment arms with non-parametric tests.

Changes from baseline in fasting blood glucose, lipid profile, anthropometric changes, inflammatory markers and cytokines will be presented by visit, treatment, and cohort.

Histology results will be presented in tabular form by treatment.

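### Withdrawing every subject with an intolerable side effect spares no further drug under single Day 0 dosing, but puts Day 28 imaging and later duration data at risk

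*Protocol*

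**What the plan says.** The withdrawal rule stands in identical words in the synopsis (Intolerable Side Effect Definition) and in Protocol Section 3.3.2: "Subjects experiencing an intolerable side effect will be withdrawn from the study, but followed for toxicity". A little earlier in the same section a softer sentence appears: "Study discontinuation is to be considered by the investigator in any case of an intolerable side effect". It does not make clear whether it means the subject or the study. Section 7.3 likewise leaves discontinuation for a Grade 3 or 4 reaction to the investigator and sponsor.

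On dosing, Section 3.3.1 states: "The dosing regimen will be a single dose treatment injection of RZL-012 in multiple sites". Section 6.2.3.1 places the injection at the baseline visit, Day 0.

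On assessments, thermal imaging after dosing is on Days 1, 7, 14, 21, 28 and 56, with later imaging in cohorts 3 and 4 (Section 6.1.12). For MRI, Section 6.1.17.2.2 says: "MRI will be evaluated in all groups at baseline and at Day 28". Further scans follow on Day 56 in cohort 2 and every 28 days in cohorts 3 and 4 (Section 6.1.13).

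On missing subjects, Section 5.4 says that in cohorts 3 and 4 "any withdrawal or removal not due to intolerable side effects within the first 28 days will be replaced by a new subject". In cohorts 1 and 2 a single withdrawal is not replaced. Section 10.6 and SAP 5.6.9 rule out imputation.

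**The concern.** Withdrawing a subject usually protects him by stopping treatment. Here there is no treatment left to stop, so toxicity follow-up alone gives him nothing that full follow-up would not. What can be lost is information.

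Section 4.1 defines the efficacy effect as one apparent at least 28 days after injection, and Section 10.1 gives the aim as finding the tolerated dose with the largest effect. Escalation continues "as long as no more than one subject experiences intolerable side effects in the lower-dose cohort", so a cohort with one such event still counts as tolerated and its Day 28 data inform the dose choice. The same data feed the efficacy look after each cohort (Section 10.7).

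A value missing for this reason is tied to a post-dose outcome. Some of the graded reactions (erythema, induration; Section 3.3.2) arise at the site whose temperature is the endpoint, so missingness at random cannot be taken for granted. Duration is affected too. Section 10.5.5 and SAP 5.8.4 present it only "for subjects in the active arm with thermogenic effect at the Day 28 visit", so a subject with no Day 28 image cannot enter that summary at all. Section 5.4 shows that the sponsor wants complete Day 28 data in cohorts 3 and 4, yet it leaves out this one cause of loss.

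**Working it through.** **Planned numbers.** Four cohorts × (6 active + 2 placebo) = 32, that is 24 active and 8 placebo. This reproduces Section 10.3. The documents give no power, effect size or dropout rate, so there is no further figure to reproduce.

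**What remains if withdrawal ends scheduled assessments** (Sections 6.1.12 and 6.1.13):

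| Last visit attended | Post-dose thermal images kept | Post-dose MRI |
|---|---|---|
| Day 7 | Days 1, 7 | none |
| Day 14 | Days 1, 7, 14 | none |
| Day 21 | Days 1, 7, 14, 21 | none |
| Day 28 | Days 1, 7, 14, 21, 28 | Day 28 |

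Withdrawal before Day 28 therefore leaves some thermal data but no scheduled post-dose MRI. The Day 28 cytokine sample in cohorts 2 to 4 (Section 6.1.8.4) is exposed in the same way.

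**Largest loss in a cohort that proceeds.** At most one subject may have an intolerable side effect. That is one of six active values (1/6 = 16.7%) or one of two placebo values (50%), not both.

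**Effect on the active-arm responder percentage.** Let k of 6 be true Day 28 responders.
- Responder lost: (k−1)/5 − k/6 = (k−6)/30. This runs from −16.7 points (k = 1: 1/6 becomes 0/5) to 0 (k = 6).
- Non-responder lost: k/5 − k/6 = k/30. This runs from 0 (k = 0) to +16.7 points (k = 5: 5/6 becomes 5/5).
- Example, k = 3, with exact (Clopper-Pearson) 95% intervals: 3/6 = 50% (12–88%) becomes 2/5 = 40% (5–85%) or 3/5 = 60% (15–95%).

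The intervals are for illustration. The plan gives only number and percent for responders, and specifies exact intervals for safety incidences (Section 10.5.4).

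**How often.** No event rate is given. If each active subject had an assumed risk q of an event before Day 28, the chance of exactly one event in six is 6q(1−q)^5:
- q = 5%: 23%
- q = 10%: 35%
- q = 20%: 39%
- q = 30%: 30%

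These are assumptions, shown only to indicate that five active values at Day 28 would be an ordinary outcome under the rule.

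**The case against.** Several points on the other side are sound.

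- **Day 28 is not the only readout.** Section 6.1.17 evaluates response every 7 days to Day 28, Section 6.1.17.1.2 speaks of an effect by Day 28, and the tables are by visit. In the phase 0 trial the rise was mostly seen at Day 14 or 21 (Section 1.2.4). A subject withdrawn in week 3 still contributes. A reader might infer that the rule removes him from the efficacy analysis; it does not.
- **The protocol already mitigates.** The termination visit includes an evaluation of response (6.2.6), unscheduled visits may include any procedure (6.2.7), Section 7.3 leaves room for judgement, and final evaluations are to be attempted whatever the cause (11.1). This makes loss a risk, not a certainty. However, a termination visit takes place at withdrawal, and none of these provisions fixes an assessment at Day 28.
- **The image may be hard to read.** Section 4.1 requires an effect unrelated to inflammation, and skin temperature after a severe local reaction may reflect inflammation. This stands for local events. It does not apply in the same way to liver-enzyme events or to MRI.
- **Six subjects say little with or without the sixth.** The intervals above overlap almost wholly. A reader might go further and infer that one loss makes significance unattainable, since the smallest chi-square Kruskal-Wallis p rises from 0.0455 (6 v 2) to 0.0528 (5 v 2). The documents do not support that as a harm: analyses are mainly descriptive with nominal p-values (Section 10.5.1), and an exact test cannot go below 0.0714 even with all eight subjects.
- **Caution about safety is reasonable, and the protocol version may differ.** The synopsis carries number 001.2, while the SAP cites V1.4 of March 2018, so the wording in force should be checked. Neither point defeats the concern, because continued observation adds no drug exposure.

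**Conclusion.** The point holds in a limited form, as a cheap improvement. Under single Day 0 dosing, mandatory withdrawal protects no one from further drug. For an event before Day 28 it puts at risk the Day 28 thermal image, the first post-dose MRI and all later duration data, with no replacement or imputation. Up to one of six active values, or one of two placebo values, can be missing in a cohort that proceeds. The resulting shift in the active responder percentage is at most 16.7 points in either direction.

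The direction of any bias is unknown, and the consequence is a weaker dose-level summary rather than a different test result.

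The conclusion rests on two readings: that withdrawal ends scheduled efficacy assessments, which no text contradicts outright, and that dosing is single as in the main text. Footnote f of the schedule (Protocol Appendix I and SAP 5.4.4) describes the cohort 4 dose as split into two clusters two weeks apart. If that were true, withdrawal could prevent a second exposure there, so it should not be said without that limit that withdrawal never spares exposure.

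**What to change.** In the synopsis and Section 3.3.2, replace the withdrawal sentence along these lines: *An intolerable side effect does not by itself end scheduled data collection. Thermal imaging, MRI and laboratory visits continue on the cohort's planned schedule unless the subject declines or the investigator judges a procedure unsafe for him. No biopsy is required. The event counts in the stopping rule and in the primary safety endpoint.*

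- The schedule meant is Day 28 and Day 56, plus later imaging in cohorts 3 and 4 where planned. Stopping at Day 28 would not be enough, because duration is measured after it.
- Record any local reaction present at each thermal image next to that image. The Draize score is already scheduled for this.
- Bring the sentence on considering discontinuation, and Section 7.3, into line.
- Resolve footnote f. If cohort 4 dosing really is split, state that no second cluster is given after an intolerable side effect.

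The cost is a wording change and a small extra visit burden for affected subjects, who may opt out. The visits are already planned, and Section 9.5.1 already keeps such subjects in contact: "ADRs graded > 1 will be followed-up until resolution, or for a maximal duration of 6 months after RZL-012 injection".
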